#### **Abstract**

Background and Rationale: A majority of neurodegenerative dementing disorders, including Alzheimer's disease, (AD), dementia with Lewy bodies (DLB) and chronic traumatic encephalopathy (CTE), now appear to be caused by the accumulation and aggregation of proteins that cause progressive damage to the brain. Recent preclinical results suggest that clearance of such neurotoxic proteins from the brain may be greatly increased during states where noradrenergic (NA) tone is decreased or blocked, such as anesthesia and normal sleep, but impaired in animal models of Traumatic Brain Injury (TBI). These results also suggest that clearance through this mechanism, which has been termed the 'glymphatic' system, is likely to be decreased in conditions where NA signaling is inappropriately maintained during sleep, such as posttraumatic stress disorder (PTSD).

Importantly, the rate at which toxins are cleared through the glymphatic system has been found to be under alpha-1 adrenergic receptor (AR) control, and the application of noradrenergic blockers such as the alpha-1 AR antagonist drug, prazosin, has been shown to increase waking clearance of these proteins to levels normally found during sleep or anesthesia. This suggests two important possibilities: first, that conditions in which the brain NA signaling is increased and sleep is impaired, such as posttraumatic stress disorder (PTSD) and TBI, may predispose people to decreased clearance of neurotoxic proteins associated with the development and progression of dementia; and second, that the use of prazosin may be able to prevent such effects.

Study Objectives, Specific Aims, and Hypotheses: We propose a two phase proof-of-concept pilot study in Veterans with PTSD and/or a history of mild or moderate TBI; phase I will be open label, and phase II will be randomized placebo controlled. It is hypothesized that prazosin (but not placebo) will decrease cerebrospinal fluid (CSF) concentrations of three established biomarkers of neurodegeneration: amyloid beta42 (Aβ42), total tau (tTau), and phosphorylated tau181 (p-tau181). Such a finding would be consistent with prazosin resulting in increased glymphatic clearance of neurotoxic molecules from the brain, and provide a rationale for larger scale studies of clinical evaluation of prazosin. Further, we will also characterize predictors and correlates of any observed effect, both in terms of the baseline characteristics of the participants showing an effect, and any clinical changes which correlate with change in CSF biomarkers.

Study Design: Sixty Veterans with a history of PTSD and/or mild or moderate TBI will receive either prazosin or placebo for a titration period plus 5 weeks. The first 22-37 of these participants will comprise phase I, and will receive open-label prazosin; in phase II, participants will be randomized to prazosin or placebo. CSF will be collected by lumbar puncture (LP) at pretreatment baseline and again after completion of 5 weeks of steady-dose study drug treatment. Unstable or serious medical conditions, conditions that are contraindications for LP, and conditions that are relative contraindications for the use of prazosin (hypotension, orthostatic hypotension, severe peripheral edema) will be exclusionary.

Relevance to VA Mission: If we find that prazosin increases clearance of potentially neurotoxic proteins, we will move towards confirmation in a larger sample and with additional endpoints, such as incidence of dementia. If confirmed, these results would provide the first rational pharmacologic treatment strategy for prevention of neurodegeneration and dementia following TBI and PTSD. They would also hold the potential of generalizing to the prevention of dementia related to other risk factors.

PTSD/TBI Glymphatic Protocol Version 3	VA Puget Sound IRB Protocol Template Version: 2/2015	Page 2 of 45
Revised 11/02/2018	·	

PTSD/TBI Glymphatic Protocol Version 3 VA Puget Sound IRB Protocol Template Version: 2/2015 Page 3 of 45 Revised 11/02/2018

## List of Abbreviations

ACT ADDreviations	Auditory Consent Trigrams	
ACTH	Adrenocorticotropic hormone	
AD	Alzheimer's disease	
ADRA1A	Alpha-1a adrenergic receptor	
ADRA2A	Alpha-2a adrenergic receptor	
AEs	Adverse events	
APOE	Apolipoprotein E	
AQP4	Aquaporin 4	
AR	Adrenoreceptor	
AUDIT-C	Alcohol Use Disorders Identification Test - Consumption	
Αβ	Amyloid beta	
Αβ42	Amyloid beta 42	
BDNF	Brain-derived neurotrophic factor	
BMI	Body mass index	
BP	Blood pressure	
ВРН	Benign prostatic hypertrophy	
CALHM1	Calcium homeostasis modulator 1	
CAPS	Clinician-Administered PTSD Scale for DSM-V	
CBOC	Community-based outpatient clinics	
CBTi	Cognitive Behavioral Therapy for Insomnia	
CCK	Cholecystokinin	
CNS	Central nervous system	
CoC	Federal Certificate of Confidentiality	
COMT	Catechol-O-methyltransferase	
CPRS	Computerized Patient Record System	
CPT	Cognitive Processing Therapy	
CRF	Corticotropin-releasing factor	
CRFs	Case report forms	
CRHR1	Corticotropin Releasing Hormone Receptor type 1	
CRP	C-reactive protein	
CRU	Clinical research unit	

PTSD/TBI Glymphatic Protocol Version 3	VA Puget Sound IRB Protocol Template Version: 2/2015	Page 4 of 45
Revised 11/02/2018		

CSD-E	Consensus Sleep Diary-E
CSF	Cerebrospinal fluid
CTE	Chronic traumatic encephalopathy
CVLT	California Verbal Learning Test II
CYP19A1	Cytochrome P450, Family 19 Subfamily A polypeptide 1
DLB	Dementia with Lewy Bodies
DSM-5	Diagnostic and Statistical Manual of Mental Disorders, 5th edition
DVBIC	Defense and Veterans Brain Injury Center
DVPRS	Defense and Veterans Pain Rating Scale
EKG	Electrocardiogram
EMDR	Eye Movement Desensitization and Reprogramming
FDA	Food and Drug Administration
FTLD	Frontotemporal Lobar Dementia
GAD-7	General Anxiety Disorders – 7
GAO	Government Accountability Office
GRIN2B	Glutamate receptor, ionotropic, N-Methyl D-Aspartate 2B
НА	Headache
HAM-D	Hamilton Depression Rating Scale
HIPAA	Health Insurance Portability and Accountability Act of 1996
HR	Heart Rate
IFIS	Intraoperative floppy iris syndrome
IGF-1	Insulin-like growth factor-1
IRB	Institutional Review Board
LP	Lumbar puncture
LRP-1	Low density lipoprotein receptor-related protein 1
MAO	Monoamine oxidase
MAPT	Microtubule-associated protein tau
МНР	Mental Health Professional
MIRECC	Mental Illness Research, Education, and Clinical Center
MoCA	Montreal Cognitive Assessment
mTBI	Mild traumatic brain injury

PTSD/TBI Glymphatic Protocol Version 3	VA Puget Sound IRB Protocol Template Version: 2/2015	Page 5 of 45
Revised 11/02/2018		

N3	NREM 3 sleep
NA	Noradrenaline
NCAM	Neural Cell Adhesion Molecule
NGF	Nerve growth factor
NMDA	N-Methyl D-Aspartate
NPY	Neuropeptide Y
NREM	Non-REM sleep
NSI	Neurobehavioral Symptom Inventory
OEF	Operation Enduring Freedom
OHRP	Office of Human Research Protections
OIF	Operation Iraqi Freedom
OIG	VA Office of the Inspector General
OND	Operation New Dawn
ORO	VA Office of Research Oversight
p-tau	Phosphorylated tau
p-tau 181	Phosphorylated tau 181
PCL	PTSD Checklist
PDR	Physicians' Desk Reference
PE	Prolonged Exposure therapy
PHQ-9	Patient Health Questionnaire-9
PLPHA	Post-lumbar puncture headache
PSQI	Pittsburgh Sleep Quality Index
PTSD	Posttraumatic stress disorder
PVT	Psychomotor Vigilance Test
QCC	Quantification of Cannabis Consumption
R&DC	Research and Development Committee
RCT	Randomized clinical trial
REM	Rapid eye movement sleep
SAE	Serious adverse event
SCID	Structured Clinical Interview for DSM-5
SDMT	Symbol Digit Modalities

PTSD/TBI Glymphatic Protocol Version 3	VA Puget Sound IRB Protocol Template Version: 2/2015	Page 6 of 45
Revised 11/02/2018		Ť

SLC6A2	Solute carrier family 6 member 2 (gene name)
SMs	Servicemembers
SUCLG2	Succinyl-CoA ligase subunit beta
TLEQ	Traumatic Life Events Questionnaire - Modified
TOMM40	Translocase of outer mitochondrial membrane 40
tTau	Total Tau
VA	Department of Veterans Affairs
VR-12	Veterans RAND-12
WTAR	Wechsler Test of Adult Reading

#### 2.0 Introduction

Although the exact cause of neurodegenerative dementing disorders varies, a majority of them – including Alzheimer's disease (AD), dementia with Lewy bodies (DLB), frontotemporal lobar dementia (FTLD), and chronic traumatic encephalopathy (CTE) – now appear to be caused by the accumulation of abnormal aggregates of insoluble proteins that cause progressive damage to the brain parenchyma. Recent evidence has suggested that the clearance of many such proteins from the brain may occur primarily during sleep, and may in particular be dependent on the dramatic decrease in noradrenergic (NA) tone known to occur during rapid eye movement (REM) and non-REM slow wave sleep, particularly what is most commonly referred to as stage III, or "N3", sleep.

These findings suggest that pathologic states that lead to inappropriately preserved NA tone during sleep, such as PTSD, may predispose to development of neurodegenerative dementing disorders by impairing clearance of neurotoxic proteins – but that reversal of the inappropriately preserved NA tone may be protective against this increased risk. Furthermore, these findings suggest that even in individuals without pathologically increased NA tone during sleep, further lowering of NA tone during both wake and sleep may be able to increase protein clearance above even baseline levels, and by doing so decrease the risk of AD or other forms of dementia in individuals with increased protein accumulation due to other predisposing factors, such as due to increased aberrant tau accumulation in TBI.

Prazosin is a selective α1 AR antagonist that has been used widely for many years to treat hypertension and urinary outflow restriction secondary to benign prostatic hypertrophy (BPH), and, more recently, as a treatment for trauma nightmares and other hyperarousal symptoms in PTSD and for reducing alcohol consumption in alcohol use disorders, as well as for ameliorating post-concussive headaches and managing disruptive agitation in dementia. Prazosin has long been FDA approved, is widely available as inexpensive generic preparations, and has a long track record of safety. Thus, prazosin is a rational choice for interrupting

PTSD/TBI Glymphatic Protocol Version 3	VA Puget Sound IRB Protocol Template Version: 2/2015	Page 9 of 45
Payised 11/02/2018		

# 3.0 Objectives

We are proposing an initial, biomarker-based proof-of-concept pilot trial of prazosin as a pharmacologic intervention to ameliorate PTSD and/or mild or moderate TBI as risk factors for neurodegenerative dementia. In phase I, participant will receive open-label prazosin; in phase II, participants will be randomized to double-blind prazosin or placebo. CSF A $\beta$ 42, total tau, and ptau181 will be measured prior to study drug initiation and following a titration period plus 5 weeks of steady-dose treatment with study drug. Quantitative and qualitative biologic measures likely to have predictive value for identifying individual variations in efficacy, including genetic markers, known or suspected indicators of central NA tone, and data on sleep, will also be collected.

#### **Specific Aims and Hypotheses:**

Aim 1: We will test for an effect of prazosin in decreasing CSF biomarkers of neurodegeneration and dementia. Specifically, we will test the primary hypothesis that prazosin administration over a titration period plus 5 weeks of steady-dose treatment will produce a consistent change across all groups in CSF concentrations of  $A\beta_{42}$ , total tau and p-tau181.

Aim 2: We will characterize predictors and clinical correlates of any observed effect of prazosin on the CSF concentrations of A $\beta_{42}$ , total tau and p-tau181. Specifically:

- Aim 2a: We will test the primary hypothesis that the magnitude of any observed effect will correlate across all groups with the degree of quantitative evidence of baseline sleep disruption either short total sleep time or fragmented sleep as measured by actigraphy.
- Aim 2b: We will carry out an exploratory analysis of the relationship of any observed effect
  of prazosin on both CSF biomarkers of neurodegeneration and dementia and symptomatic
  rating scales with genetic markers associated with increased risk and/or progression of
  neurologic disorders and brain injury, as well as genetic markers associated with the uptake

PTSD/TBI Glymphatic	Protocol Version 3	VA Puget	Sound IRB Protocol	Template V	/ersion: 2/2015	Page 10 of 45
Revised 11/02/2018				•		

and biologic distribution of orally consumed drugs.

• Aim 2c: We will carry out exploratory analyses of correlations between any observed efficacy of prazosin and additional baseline and post-treatment clinical assessments, including psychiatric symptom rating scales, pupillometry measurements, and baseline blood pressure and heart rate.

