If at the end of phase I the results are potentially consistent with a clinically significant effect, but do not yet meet statistical significance, we will continue the open label portion until we have enough subjects who have completed the study to increase the power from 80% to 95%. Again using a one-sample t-test with a 5% Type I error rate, this would require 15 additional completers above the 22 initially planned, or 26 subjects screened when allowing for the same expected screen failure and dropout rates.

Participant Randomization: Participants in phase II will be randomly assigned 2:1 to prazosin or

PTSD/TBI Glymphatic Protocol Version 3	VA Puget Sound IRB Protocol Template Version: 2/2015	Page 37 of 45
Revised 11/02/2018		. 1

placebo, stratified by gender and group (TBI only, PTSD only, or both). Permuted block randomization codes within each stratum will be generated by a MIRECC staff member uninvolved with this study using statistical software. This person will create one card per subject number specifying treatment assignment and will prepare double envelopes labeled with the subject number and containing the treatment group assignment card. These envelopes will be used for purposes of breaking the blind when necessitated by medical emergency when a computer and the Internet may not be available, and following study termination assessments (see section 5.7 below). In addition, the investigational pharmacist will have access to the randomization codes. No other study personnel will have access to the randomization codes.

Descriptive statistics of baseline characteristics will be calculated: demographic variables, vital signs, number and cause of TBI, mental health and substance use assessment scales, cognitive testing scores, total sleep time by participant report and by actigraphy, and sleep fragmentation index as measured by actigraphy.

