Primary outcome measures will be CSF total-tau, p-tau181, and Aβ42. For each outcome, we will use a linear regression model to compare, between treatment groups, the within-subject changes in biomarkers from baseline. The model will include concentration at study completion as the response (dependent) variable, and the concentration at baseline and treatment group as the predictor (independent) variables, along with the covariates age, gender, APOE\*4 status, and blast exposure quantification. To account for dropouts and subjects who have their final biomarker assessment prior to 10 weeks, we will also use a linear mixed-effects regression model with biomarker concentration as the response variable, and the predictor variables time, treatment group, and a time by treatment group interaction term, along with the same covariates as for the linear regression model. Exploratory analyses will be conducted of the interaction among biomarkers; sleep and ambulatory monitoring variables; participant-reported symptoms of PTSD, depression, and postconcussive symptoms; and cognition.

Data will be analyzed by co-investigator [name], with consultation as necessary with the MIRECC biostatistician, [name], regarding the analysis plan and interpretation.

Data Management: All study information will be recorded on standardized CRFs. Forms will be labeled with study code numbers only. Code numbers will be assigned sequentially, and will not include participant initials or any other personally identifiable information. Source documents, which may include identifying information, will be maintained in locked files within a locked office. The study coordinators at VA Puget Sound and Madigan will keep the key between the identity of participants and study code number. The key will not be shared with to anyone other than members of the research team.

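### Aim 1 claims a consistent effect in all groups, but the section 5.5 models estimate only one pooled treatment effect per biomarker, so an effect confined to one or two diagnostic groups could be read as holding in all.

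*Combined protocol and SAP*

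**What the plan says.** **Hypothesis.** Section 3.0, Aim 1, opens: "We will test for an effect of prazosin in decreasing CSF biomarkers of neurodegeneration and dementia". The next sentence gives the primary hypothesis, that treatment "will produce a consistent change across all groups in CSF concentrations of" the three biomarkers. Neither sentence says what the groups are or what would count as consistent. The Abstract gives the direction: "It is hypothesized that prazosin (but not placebo) will decrease cerebrospinal fluid (CSF) concentrations of three established biomarkers of neurodegeneration".

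**Strata.** The only classification of participants by diagnosis that is set up for use in the trial is in the randomization paragraph of section 5.5. There, phase II is "stratified by gender and group (TBI only, PTSD only, or both").

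**Analysis.** Section 5.5 uses a linear regression "to compare, between treatment groups, the within-subject changes in biomarkers from baseline". Its terms are "the concentration at baseline and treatment group as the predictor (independent) variables", "along with the covariates age, gender", APOE*4 status and blast exposure. The mixed model has "the predictor variables time, treatment group, and a time by treatment group interaction term" with the same covariates. The exploratory list in that section does not mention diagnostic group. Phase I is sized on a one-sample t-test over all completers.

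**The concern.** The hypothesis makes a claim about every group, while the analysis yields one number averaged over groups. Nothing in section 5.5 could show that the effect is similar across the diagnostic strata, or that it is not. Gender, the other stratification factor, is in the model; diagnosis is not, even as a main effect.

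The protocol's own rationale makes different responses plausible. Section 2.0 describes reversing abnormally preserved noradrenergic tone in PTSD, but lowering tone further in people without that abnormality, with TBI as its example. Aim 2a expects response to vary with baseline sleep disruption. The Abstract and the risk-benefit discussion in section 5.0 draw conclusions for both TBI and PTSD, and the Abstract plans a larger confirmatory study. If a pooled finding is worded as Aim 1 is, readers could carry it over to a group in which nothing happened.

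**Working it through.** **Inputs from section 5.5.** Baseline mean 294 ng/L, baseline SD 54, within-person correlation 0.98, phase II completers 40 prazosin and 20 placebo, two-sided 5% test, target difference about 5%.

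**The plan's own figures.**
- SD of change = 54 × √(2 × (1 − 0.98)) = 10.8 ng/L, which reproduces.
- Difference = 0.05 × 294 = 14.7 ng/L.
- At SD 10.8, 40 against 20 gives 99.8% power by the noncentral t, not the stated 90%. An SD of about 16.3 gives 90%. That mismatch is a separate matter. Both SDs are used below so that the result does not depend on it.

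**Assumption.** The documents give no group shares. Near-equal thirds are assumed: 13/13/14 on prazosin and 7/7/6 on placebo.

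**Pooled test when the effect is not shared.** The test is a two-sample t-test on change, the test named in the power text. The ANCOVA residual SD, 54 × √(1 − 0.98²) = 10.75, is almost the same as 10.8. Simulation gives:

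| True effect | Pooled test significant, SD 10.8 | SD 16.3 |
|---|---|---|
| 5% fall in two groups, none in the third | 83% | 52% |
| 5% fall in one group only | 26% | 15% |
| 10% fall in one group only | 62% | 39% |
| 15% fall in one group only | 86% | 62% |

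The simulation error is one to two points.

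**Hand check of the first row at SD 10.8.**
- Pooled effect = (26/40) × 14.7 = 9.56 ng/L.
- The unmodelled spread between groups adds 14.7² × 0.65 × 0.35 × 40/58 = 33.9 to the pooled variance: 116.6 + 33.9 = 150.5.
- Estimated SE = √(150.5 × (1/40 + 1/20)) = 3.36. The cut-off is 2.00 × 3.36 = 6.73.
- True SE = 10.8 × √0.075 = 2.96.
- (9.56 − 6.73)/2.96 = 0.96, a probability of about 83%.

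**What a group analysis can and cannot show at 60 completers.**
- SE of a group-specific effect = SD × √(3/40 + 3/20) = 0.474 × SD, or 5.1 and 7.7 ng/L. With t = 2.005 on 54 df, the 95% half-widths are 10.3 and 15.5 ng/L, which are 3.5% and 5.3% of 294.
- Treatment-by-group F test (2 and 54 df), 5% fall in one group only: noncentrality = 14.7² × (2/3)/(0.225 × SD²) = 5.49 at SD 10.8 and 2.41 at 16.3. Power is about 52% and 25%. By symmetry it is much the same for falls in two groups (simulated 51% and 26%).
- If every group truly falls by 5%, each is individually significant with probability 78% or 44%, and all three with probability 0.78³ ≈ 48% or 0.44³ ≈ 9%. Significance in each group is therefore not a usable test of consistency.

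**The case against.** **Meaning of the groups.** Aim 1 does not define them. Aim 2a uses the same phrase for a correlation, where it may mean no more than pooled over the whole sample. On that reading the model fits the hypothesis and the fault is loose wording. This is possible, but the word consistent then does no work, and the only diagnostic strata set up for the trial are those in the randomization paragraph. Either reading calls for a definition.

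**Direction.** A reader might infer that, because the hypothesis sentence says change and phase II is tested two-sided, a significant rise would satisfy Aim 1. The documents do not support that. The sentence immediately before says the aim is to test for decreasing biomarkers, and the Abstract and the power text also say decrease. A rise would contradict Aim 1. A two-sided test of a directional hypothesis is ordinary.

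**Size.** A reader might also infer that an effect in one group would regularly produce a positive trial. That takes a large effect: about 15% in one group and zero elsewhere to reach 62–86%, three times the protocol's 5% threshold. At 5% in one group the pooled test usually misses it. The more realistic risk is two groups responding and one not.

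**Pilot status.** This is a proof-of-concept study with confirmation planned, and Aim 2 looks at predictors of response. That lowers the stakes. It does not close the gap: sleep, genetic, symptom and autonomic correlates do not give the treatment effect in, say, participants with TBI only. Nor do the documents show that a later study would recruit the wrong population.

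**Conclusion.** The point holds as a mismatch between the stated primary hypothesis and its analysis. Followed as written, section 5.5 can support an average effect over the enrolled mix but not consistency across TBI only, PTSD only and both. A pooled result could be over-read in this way; it need not be. With 5% falls in two of three groups, the pooled test is significant in about 52% to 83% of trials; with a 5% fall in one group, about 15% to 26%. These figures assume equal thirds, 40/20 completers and an SD of change between 16.3 and 10.8 ng/L. Unequal shares would change them.

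The absence of group terms is read directly from the text and does not depend on the simulation. The direction is adequately stated elsewhere, so the word change is only a matter of alignment. The trial is too small to prove consistency by any analysis. What can be corrected is the claim and the reporting.

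**What to change.** 1. **Aim 1.** Define the groups as the three randomization strata. State the primary hypothesis as an average between-arm decrease in each biomarker. Writing decrease in that sentence only aligns it with the rest of the protocol.
2. **Section 5.5.** Add diagnostic group to the primary model as a stratification factor. Add one supporting model per biomarker with a treatment-by-group interaction, reporting the three group-specific treatment effects with 95% CIs. For phase I, report mean change by group with CIs.
3. **Interpretation.** Describe the primary result as an average effect. Discuss consistency only from the group estimates and their CIs. State in advance that a non-significant interaction at 60 completers does not establish consistency.

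**Cost.** No extra participants or data, since the stratum is recorded at randomization. It takes one more model per biomarker and two degrees of freedom in the primary model. The group intervals will be wide (half-widths of roughly 10 to 16 ng/L under the assumptions above), and the claim is somewhat narrower than Aim 1 now makes. The change should be made before any phase II data are unblinded. Section 5.6 breaks the blind for each participant at completion, so that point comes early.
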